7.0 Risks

Drawing of venous blood: Puncturing of a vein may result in minor bleeding or bruising. Because some people may faint during blood draw, we will ask the participants to lie down during blood collection.

Fasting: Dizziness, light-headedness, or nausea can occur as result of fasting.

75gr OGTT: nausea, vomiting, or light-headedness may occur after drinking the glucose solution. A drop in blood glucose levels may occur during the test which may cause nausea, dizziness, sweating, weakness, or restlessness. A significant drop in glucose levels during the test is likely to occur during illnesses, alcohol consumption, dieting, in patients using medications or long periods of bed rest (hospitalized patients), but rarely in healthy people. The study team will monitor the blood glucose several times during the test using a glucometer. If blood glucose levels fall out of safe ranges, the test will be stopped and oral (or intravenous) glucose solutions will be administered if needed. Transient hyperglycemia during OGTT is likely to occur in people with undiagnosed diabetes, and it resolves spontaneously once the test is complete.

Prednisone is a FDA-approved drug for several disorders. Glucocorticoids have several side effects (e.g., increase in blood pressure, electrolytes abnormalities, adrenocortical suppression, risk of infection, mood and behavioral disturbance, gastrointestinal problems, etc.), which are more likely to occur with repeated and high doses. We plan to administer a single dose of prednisone 60 mg to healthy individuals and monitor them for the next 6-6½ hours after the administration of the drug. It is unlikely that any harmful side effects will occur with a single exposure to

glucocorticoids. Prednisone has a half-life of 18-36 hours; thus, we will instruct all the participants to contact us if they experience any discomfort within the next 72 hours after the study conclusion.

8.0 Reporting of Adverse Events or Unanticipated Problems involving Risk to Participants or Others

The proposed study is low risk. These studies do not fall into the traditional Phase I, II, or III clinical trial concepts. Nevertheless it is important to monitor the data obtained and subject safety. Monitoring should be commensurate with the risks, which are small. The principal investigator proposes to review the data weekly and adverse events if they occur. During the conduct of the study, any serious adverse event will be reported to the IRB within 7 days of the PI's notification of the event. Should the risk-benefit ratio of the study change the principal investigator will make alterations to the procedures of the study and submit them to the IRB.

9.0 Study Withdrawal/Discontinuation

Withdrawal of participants from any part or the whole study is under the discretion of the PI and will be done if:

- Performing a specific study procedure may be harmful for the participant or he/she cannot tolerate the procedure.
- The participant does not meet the study requirements
- The study is stopped
- Participant is not willing to continue the study

Participants who may not tolerate the OGTT may continue in the study to assess GC efficacy but not GC metabolic toxicity. The study team will explain to the participant why he/she is taken out from specific procedures or from the whole study.

10.0 Statistical Considerations

Although this is a pilot study that will provide preliminary information of the effect size and variability of our outcomes (clinical and gene expression changes), we have 85% power to detect a minimum fold change of 2.5 for a total number of 20,000 tested genes with the top 100 being prognostic with a FDR of 0.1 using exact test, assuming a minimum average read counts of 10 for prognostic genes, a maximum dispersion of 0.5, and a ratio of the geometric mean of normalization factor of 1. The main analysis of the gene expression data will be carried out by [name] (VANGARD), who will perform the following procedures:

- Detect genes that on average change expression levels due to GC treatment: we will normalized gene expression data. We will use the \log_2 fold change in expression as a measure of response, and perform multiple linear regression controlling for potential covariates (batch, age, and BMI) with a FDR < 0.1.
- Identify a set of genes with expression patterns are predictive of GC response: to test the association between changes in our clinical outcomes (lymphocyte counts and metabolic indexes) and \log_2 fold change for each gene, we will perform linear regression analysis using a FDR of 0.1. We will stratify our analysis by sex. To control for the effect of estrogens levels in GC response among females, we will register the day of the menstrual cycle that the study visit occurred and include it as a covariate. For women

who are using a hormonal birth control method, we will also include the type of hormone birth control method (systemic or local), and active ingredient (progesterone with and without estrogen) as covariates.

- Select a list of candidate of regulatory variants that are likely to explain the observed variability in gene expression patterns: using public available eQTL datasets (GTEx, seeQTL, NCBI eQTL Browser, Genevar, SCAN, ExSNP, etc), we will query genes that their gene expression profile are predictive of GC response to identify a candidate list of variants for genome interrogation. We will select variants that: (a) have shown to be significantly associated with the expression of the respective gene ($P < 5 \times 10^{-4}$), (b) are located within 1 megabase on either site of the gene's transcriptional start site, and (c) have MAF > 0.10 . We will combined genome information and the gene expression data using a Bayes factor calculation²⁷ to identify which variants do affect gene expression profile with GC administration with and without OGTT.

Additionally, to determine which mechanisms are shared between in *in vivo* and *in vitro* GC exposure, we plan to culture PBMCs with GC in normoglycemic and hyperglycemic media. PBMCs will be isolate from blood samples collected at screening visit and culture for 4 hours with GC in a normoglycemic and hyperglycemic media to simulate the effect of OGTT and measure changes in gene expression. By comparing gene expression profiles from *in vivo* and *in vitro* administration of GC on PBMCs from the same individual, we can identify which mechanisms are shared in both conditions. This will largely improve our ability to perform clinical studies in the future that involve GC exposure by reducing the risk and costs related to drug exposure for specific mechanisms that are shared in *in vitro* and *in vivo* response.

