GCs are known to exert their effect through changes in gene expression and also by interacting with several transcription factors,^{26,27} but we still do not know which genes are involved in the response to *in vivo* administration GC in humans, and which genetic variants are more likely to affect the expression of these genes. Thus, we propose **to perform a hypothesis-generating pilot study to identify potential set of genes and**

regulatory variants that are likely to be involve in the response to GC in terms of efficacy and metabolic toxicity.

For this pilot study we plan to use a robust pharmacodynamic effect of GCs (GC-induced lymphopenia) and a common metabolic complication of GC therapy (GC-induced glucose intolerance) after *in vivo* administration of GC as our clinical phenotypes to:

Specific Aim: To characterize gene expression patterns that are predictive of *in vivo* GC response, and identify regulatory variants that are associated with *in vivo* GC response by challenging 40 healthy volunteers with 60 mg of oral prednisone. We will measure changes in lymphocyte counts and changes in glucose regulation (using the 75 gr glucose tolerance test ~ OGTT) as surrogates of GC efficacy and metabolic toxicity. We will perform transcriptome-wide next generation RNA sequencing to measure changes in gene expression due to *in vivo* administration of GC and study the association of gene expression patterns with our clinical phenotypes. Once we identify a set of genes that are significantly changed after *in vivo* GC administration, we will select potential regulatory variants that have been associated with changes in expression of these genes in public available expression quantitative trait loci (eQTL) datasets to perform genome interrogation and eQTL analysis. This will allow us to identify variants that are associated with gene expression changes due to *in vivo* administration of GC.

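### Effect estimates for FDR-selected genes will be overstated on average, mainly in the sex-stratified associations, and section 10.0 plans no correction

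*Combined protocol and SAP*

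**What the plan says.** Section 10.0 names effect size and variability among the pilot's products: "this is a pilot study that will provide preliminary information of the effect size and variability of our outcomes (clinical and gene expression changes". The sample in section 2.0 comes from "challenging 40 healthy volunteers with 60 mg of oral prednisone".

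Section 10.0 then sets out two gene-level screens.

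- **Average change.** Log2 fold change is regressed with adjustment for batch, age and BMI, and genes are kept at FDR below 0.1. This bullet names no sex stratification.
- **Association with clinical response.** Changes in lymphocyte counts and metabolic indexes are related to each gene's log2 fold change: "we will perform linear regression analysis using a FDR of 0.1. We will stratify our analysis by sex". Among women, cycle day and contraceptive details enter as covariates.

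The genes that pass the second screen go on to a search of public eQTL datasets. Section 10.0 names no shrinkage, cross-validation, bootstrap or replication sample for the estimates of the selected genes. The documents give no split or quota by sex.

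**The concern.** When a gene is reported because its estimate crossed a threshold, and the same data supply the estimate, the reported size is biased upward (the winner's curse). This is separate from power: it concerns how large the effects look among the genes that are found. The less power a gene had, the larger the bias, because only a lucky draw carries it over the line.

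This matters because effect size is a stated product of the pilot. If the raw figures for selected genes were taken at face value, weak and moderate associations would look alike and strong. Anyone who planned later work on them would plan too small.

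**Working it through.** **Inputs.** From section 10.0: "we have 85% power to detect a minimum fold change of 2.5". The same sentence sets 20,000 genes, of which 100 are truly prognostic, an FDR of 0.1 and an exact test. Its floor gene has a mean count of 10 and a dispersion of 0.5, and the normalization ratio is 1. From section 2.0: 40 participants. Assumed: 20 per sex, two-sided tests, bivariate normal data and no covariates in the association model.

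**Step 1: per-gene level.** The plan's inputs imply 0.85 × 100 = 85 true discoveries, so alpha = 85 × 0.1 / (19,900 × 0.9) = 4.75e-4. That corresponds to 85 / 0.9, or about 95 listed genes.

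**Step 2: the plan's own figure.** A two-group negative-binomial exact test at this level gives power of 97.2% with 40 per condition, 61.3% with 20, and 84.4% with 28. The stated 85% is thus not reproduced at 40 or 20. The sentence attaches no sample size, so this does not show an error. The figure concerns mean fold change and says nothing about the associations.

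**Step 3: cut-off for a listed association.** |r| = t / sqrt(t² + n − 2).

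- n = 20: t = 4.257, so |r| = 4.257 / sqrt(18.12 + 18) = 0.71.
- n = 40: t = 3.824, so |r| = 3.824 / sqrt(14.62 + 38) = 0.53.

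Under the Benjamini-Hochberg rule the n = 20 cut-off depends on how many genes are listed: 0.60 with 1,000, 0.71 with 95, and 0.83 with one. Four extra covariates (also an assumption) would raise 0.71 to a partial |r| of 0.77.

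**Step 4: mean reported r among listed genes** (400,000 simulated samples per row, alpha = 4.75e-4).

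| True r | n = 20: listed | n = 20: reported r | n = 40: listed | n = 40: reported r |
|---|---|---|---|---|
| 0.4 | 3% | 0.75 | 17% | 0.59 |
| 0.5 | 9% | 0.76 | 43% | 0.61 |
| 0.6 | 23% | 0.77 | 76% | 0.64 |
| 0.7 | 51% | 0.79 | 96% | 0.70 |
| 0.8 | 84% | 0.82 | >99% | 0.80 |
| 0.9 | 99% | 0.90 | >99% | 0.90 |

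At n = 20, the reported value hardly distinguishes a true r of 0.4 from 0.6. At true r 0.8, 36% of listed estimates fall below the truth; at 0.9, 45% do. At the looser level 0.005 (1,000 listed, n = 20), true r 0.4 is reported as 0.67 and 0.5 as 0.69.

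**Step 5: average change, all 40.** Take the plan's floor gene and treat the visits as independent. On the natural-log scale, SE = sqrt((1/40)(1/10 + 1/25 + 2 × 0.5)) = 0.169. The threshold is 3.495 × 0.169 = 0.59, a 1.80-fold change. The mean of the estimate given that it passes is:

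- true 2.5-fold: reported as 2.53;
- true 2-fold: reported as 2.16;
- true 1.5-fold: reported as 1.97, and called 14% of the time.

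A variant with SE = sqrt(2 × (1/10 + 0.5)) / ln 2 / sqrt(40) = 0.25 and threshold 0.96, in log2 units, gives 2.57 for a true 2.5-fold change. A true 1.5-fold change is reported as about 2.1, and called 7% of the time.

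**Step 6: illustration of use in planning.** n = ((1.96 + 0.84) / atanh r)² + 3, for 80% power at two-sided 0.05. A study sized on r = 0.76 needs 11 people. If the true r is 0.5, its power is 34%, and 30 would be needed. With the pooled estimate of 0.605, 19 are planned and power is 59%.

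**The case against.** The strongest reply is that this is a hypothesis-generating pilot. Its listed genes feed an eQTL search that uses their identity, not their effect size. The sentence on effect size speaks of clinical and expression changes and does not name gene-phenotype slopes. Nothing says that only selected genes will be reported. The worst-affected genes are seldom listed: at n = 20 a true r of 0.4 passes about 3% of the time, so 85 true discoveries would need roughly 85 / 0.032, or about 2,650, such genes. The fold-change check uses the plan's least favourable gene and ignores pairing; positive within-person correlation would shrink the bias.

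All of that stands and limits the point. It does not remove it, because expression changes are named as an effect-size product, selection and estimation share the same people, and no correction is named. The bias also persists across the plausible range of cut-offs and when the sexes are pooled.

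A reader might infer more than the documents support:

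- **That every listed gene is greatly inflated.** The bias depends on each gene's power. It is about 6% in log fold change at 85% power and near zero for strong effects, and single estimates can fall below the truth.
- **That all gene results rest on about 20 people per sex.** The split is not stated, and the stratification sentence sits only in the association bullet.
- **That a follow-on study will be underpowered.** No such study is planned on these estimates; step 6 is only an illustration.
- **That the clinical effect sizes are biased too.** They are not selected by FDR.

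**Conclusion.** The point holds in limited form. Estimates for FDR-selected genes will be overstated on average, and section 10.0 names no remedy. The bias is large for weakly powered genes in the sex-stratified associations, where a true r of 0.4 to 0.6 is reported as 0.75 to 0.77. It is moderate for a true r of 0.4 with all 40 pooled (about 0.59). It is small for r of 0.8 or more at n = 20, and for a 2.5-fold mean change in 40 (reported as about 2.5 to 2.6). The association figures rest on an assumed even split by sex, a per-gene level of 4.75e-4 and a model without covariates. This is a gap in estimation and reporting that is worth closing; it does not invalidate the design or the choice of screens.

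**What to change.** Add to section 10.0: *Log2 fold changes and gene-phenotype slopes or correlations will be reported for all tested genes, with empirical-Bayes shrinkage or with a bootstrap or cross-validation correction that repeats the gene selection in each resample. Uncorrected estimates for FDR-selected genes will be labelled as subject to selection bias and will not be used alone to size later studies.*

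This needs no new participants, samples or procedures. The cost is a little more computation on the same data and less favourable reported effects.

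### The regression of lymphocyte-count change on gene expression has no cell-composition term, so a cell-type marker can look predictive; a side-by-side sensitivity model is a cheap improvement

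*Combined protocol and SAP*

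**What the plan says.** Section 10.0 sets out a chain of analyses.

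- **Step 1** is to "Detect genes that on average change expression levels due to GC treatment". It takes the log2 fold change as the response and will "perform multiple linear regression controlling for potential covariates (batch, age, and BMI) with a FDR < 0.1".
- **Step 2** is "to test the association between changes in our clinical outcomes (lymphocyte counts and metabolic indexes) and" the log2 fold change of each gene, by linear regression at an FDR of 0.1. The plan adds "We will stratify our analysis by sex". The only covariates named for this step are cycle day and hormonal contraception in women.
- **Variant selection** follows: "we will query genes that their gene expression profile are predictive of GC response to identify a candidate list of variants for genome interrogation".

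Section 6.0 takes RNA from PBMC lysates at both study visits. It describes neither sorting nor estimation of cell proportions. Its measurement list includes blood cell counts but does not say that a differential is taken. Section 3.0 states that glucocorticoids act partly by altering immune-cell traffic, and that leukocytes other than neutrophils and lymphocytes fall sharply, sometimes below detection.

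The Specific Aim in section 2.0 begins "To characterize gene expression patterns that are predictive of" in vivo response, so the step 2 list is a result in its own right. The same aim describes the route to variants differently from section 10.0: "Once we identify a set of genes that are significantly changed after" in vivo dosing, "we will select potential regulatory variants that have been associated with changes in expression of these genes".

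**The concern.** A PBMC lysate is a mixture, and its log2 fold change combines two things: change in expression within cells and change in the proportions of cells. By the protocol's own account the drug moves the proportions.

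In step 2 with the lymphocyte outcome, both sides of the regression then depend on the same cell movement. Someone whose lymphocytes fall further than average will have a higher monocyte share, unless monocytes fall in step. Monocyte markers will read higher in that person although no gene has been regulated.

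What is at stake is how the list is read. Genes reported as predictive of response could partly be markers of cell redistribution, and they go on to variant selection with no check in between.

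**Working it through.** **The plan's own figure.** Section 10.0 gives one power statement: 85% power, fold change 2.5, 20,000 genes of which 100 are prognostic, FDR 0.1, mean count 10, dispersion 0.5. It describes a differential-expression test (step 1). Treated as an unpaired two-group negative binomial test, 40 per condition gives about 97% power; 85% corresponds to about 28 per group. That does not bear on this point. No power, number of true genes or list size is stated for step 2.

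**Illustrative per-gene alpha.** Borrowed from that statement: expected false positives = 85 × 0.1/0.9 = 9.44; alpha = 9.44/19,900 = 4.7e-4. This is a convenience, not a planned step 2 threshold.

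**Mechanism by hand.** Assume PBMCs are 80% lymphocytes and 20% monocytes, and take genes with no regulation. A monocyte-only gene has log2FC = log2(f2/f1), where f is the monocyte fraction.

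| Lymphocytes fall | Monocytes fall | f2 | Monocyte-only gene, log2FC | Gene 3-fold higher per monocyte | Lymphocyte-only gene |
|---|---|---|---|---|---|
| 70% | 50% | 0.10/0.34 = 0.294 | +0.56 | +0.18 | -0.18 |
| 30% | 50% | 0.10/0.66 = 0.152 | -0.40 | -0.10 | +0.08 |
| 70% | 70% | 0.06/0.30 = 0.200 | 0 | 0 | 0 |

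Monocyte markers move most, partial markers much less, and nothing moves if the subsets fall in parallel.

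**Simulation of step 2.** Inputs from the documents: 40 participants, analysis by sex, regression on log2 fold change. Everything else is assumed: an even split (n = 20 per sex); lymphocytes down 50%; monocytes down 50% or 80%; log-normal falls with SD 0.25, 0.4 or 0.6; expression noise SD 0.3 log2; no regulation. A gene counts as selected if p < 4.7e-4, so the nominal rate is 0.05%.

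| Setting, planned model | Correlation of the two falls | Selected |
|---|---|---|
| Monocyte-only gene, log change in count | 0-0.5 | about 2-45% |
| Same | 0.8 | 0.2-0.8% |
| Same | 1 (parallel) | near nominal |
| Monocyte-only gene, absolute change, baseline log-SD 0.3 | 0-0.5 | about 0.3-24% |
| Gene 3-fold higher per monocyte, log change | 0-0.5 | about 0.1-5.5% |

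The low ends come from small between-person variation and correlation 0.5, the high ends generally from large variation and independent falls. A separate simulation with other assumptions (independent falls only) gave 7-75% for a monocyte marker at n = 20.

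**With the change in log2 monocyte fraction added**, log-change scale, correlation 0-0.5:

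| Source of the fraction | Monocyte-only gene selected |
|---|---|
| Known exactly | under 0.1% |
| Differential count, log error SD 0.07 (lymphocytes), 0.15 (monocytes) | 0.3% or less |
| Differential count, monocyte error SD 0.5, monocytes down 80% | about 1-8% |

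**The case against.** The strongest reply is that the size is built from inputs the documents do not give, and that the larger figures use unfavourable ones. Much of this stands.

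- Section 10.0 does not say whether the lymphocyte change is absolute or relative, and the absolute scale roughly halves the top of the range.
- Everyone receives the same dose, and the protocol describes the response as concentration-dependent. Shared exposure could make the two falls correlate strongly, in which case the effect nearly vanishes.
- The large figures apply to genes expressed only in monocytes.
- The sensitivity model depends on count precision. Section 3.0 warns of undetectable counts, and the log fraction is undefined at zero.

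A reader might infer that the nominal 10% false discovery rate becomes some specific higher share. The documents do not support any such figure: they plan no step 2 list size or power and do not say how many pure cell-type markers are tested.

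A reader might also infer that the variant findings are false. The later test relates genotype to expression. With genotype independent of cell mix, regression of log2 fold change on genotype, used as a stand-in for the planned Bayes factor, kept its size for a composition-only gene (4.8-5.2% at 0.05, n = 40), also after step 2 selection. That limits false variant findings; it does not clean the gene list.

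The planned cell cultures are a closed system and could serve as a partial cross-check, but section 10.0 uses them to find shared mechanisms, not to check step 2 genes. That this is a hypothesis-generating pilot lowers the stakes, yet a list for follow-up is exactly what such a study produces.

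**Conclusion.** The point holds as a cheap improvement to step 2 with the lymphocyte outcome. The text establishes the mechanism; its size rests on the assumed two-cell model and could range from negligible to substantial for strongly cell-specific genes.

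Two wider readings are not supported. Step 1 is not shown to be wrong: an average change in the PBMC sample is a valid total effect, provided it is described as such. Nothing is shown for the metabolic indexes, which are not cell counts.

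Separately, and with no simulation needed, sections 2.0 and 10.0 name different source lists for variant selection: genes changed by treatment in one, genes predictive of response in the other.

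**What to change.** 1. **Step 2, lymphocyte outcome only.** Keep the planned model and report beside it a sensitivity model that adds the change in PBMC cell fractions. Take the fractions from the blood-count differential of the same draw as the RNA where available, and state how very low or zero counts are handled. Do not use the lymphocyte-count change itself as the covariate, since it is the outcome.
2. **Before variant selection.** Flag genes found only in the unadjusted model as possible cell-mix markers. Remove none.
3. **Step 1.** Describe the list as the total effect on the PBMC sample.
4. **Separately.** Reconcile sections 2.0 and 10.0 on which gene list feeds variant selection.

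**Cost.** SAP wording and one extra model; no new visits, draws or cultures. The sensitivity model loses power because composition is linked to the outcome. In the assumed model (n = 20), power for a truly predictive gene falls from 35-48% to 13-40% at a gene-outcome correlation of 0.7, and from 93-99% to 67-98% at 0.9. Among truly predictive genes that the planned model selects, the flag would mark 21-69% at 0.7 and 1-27% at 0.9, which is why flagged genes stay.

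**Limits.** If no differential is taken, fractions estimated from RNA markers are the fallback, but they can be biased if glucocorticoid changes the markers. Blood counts do not resolve lymphocyte subsets.

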glucose intolerance during GC therapy is in part due to a genetic component since the degree of glucose intolerance varies markedly among patients who received the same dose of GCs;⁵⁴ there is large variability in the incidence of glucose intolerance due to GC therapy among races;^{55,56} and variants known to affect GC sensitivity have been associated with metabolic phenotypes⁵⁷⁻⁶⁵ Despite these observations, the genetic determinants of GC-induced metabolic toxicity are not known and we cannot predict who will develop a metabolic complication during GC therapy.

GC exert their effects through the regulation of gene expression by regulatory variants: GCs are known to exert their effect through changes in gene expression and by interacting with several transcription factors. Thus, they represent an excellent tool to study gene-environment interactions.⁶⁶ Accordingly, using immortalized and cultured human [peripheral blood mononuclear cells \(PBMCs\)](#), several studies have shown that GC response is associated with different patterns of transcriptional response,^{14,27,67} and that variants in regulatory binding sites at GC-targeted genes may play a role in GC response variability.^{12,14,26,27} However, the process of immortalization and the culture of cells are known to affect the gene expression response and likely differ from *in vivo* expression.⁶⁸⁻⁷⁰ Moreover, the eQTL studies using immortalized cells have little overlap with eQTL from cultured cells.²⁷ To our knowledge, there is only one small study that has examine gene expression changes with *in vivo* administration with GC but have not performed eQTL analysis. Olnes explored genome transcription response after *in vivo* administration of GCs using whole transcriptome microarrays,⁷¹ and found that peak changes in gene expression were observed 4 hours after GC administration with large variability in the gene expression changes. We propose to extend Olnes' work by studying the role that genetic variants have in the observed variability of gene expression response during *in vivo* administration of GC. Besides, we propose to study PBMCs gene expression response to a glucose challenge due to *in vivo* administration of GCs to study the genetic architecture of the metabolic complications of GC administration, which has not be done.

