- Study visit 1: The participant will arrive fasting early in the morning to VUMC. A standardized clinical interview and brief physical examination will be performed. For female participants, a urine sample will be collected for pregnancy testing. A fingerstick will be performed to check fasting glucose level. An intravenous catheter will be placed in one arm for continuous sampling around 3 1/2 hours after the participant arrival. Once venous access is secure, blood samples will be collected at different times. If the fasting glucose is ≥ 126 mg/dl, the participant will be excluded from the oral glucose tolerance test study, and blood will be collected approximately 4 and 6 hours after the fingerstick. If blood glucose is below 126 mg/dl; we will collect blood samples around 4 hours after the patient's arrival. Immediately afterwards, a 75-gram glucose solution will be administered as part of the oral glucose tolerance test (OGTT), and blood samples will be collected at 10, 20, 30, 60, 90, and 120 minutes after glucose ingestion. Participants with 2-hour blood glucose ≥ 200 mg/dl will be excluded. A standard meal will be provided at the end of the study visit.
- Study visit 2: Visit 2 will occur within one month after visit 1. An interview, physical exam, and urine testing in the fasting participant will be performed, as in Study visit 1. A single dose of 60 mg of oral prednisone will be administered immediately after a fingerstick for blood glucose is performed. Approximately 3 1/2 hours later, an intravenous catheter will be placed in one arm for continuous sampling. The first blood

collection will be performed around 4 hours after the ingestion of prednisone, and immediately after an OGTT will be performed (if tolerated on study visit 1). Blood collection will occur at 10, 20, 30, 60, 90, and 120 minutes after glucose ingestion. A standard meal will be provided at the end of the study visit.

Each visit will take approximately 6 hours and the participant should stay at VUMC during the study visits. The study team will contact the participant by phone for the next two consecutive days after the last visit to inquire about any problem related to the study.

Measurements: Blood samples will be used for the following:

- Basic metabolic screening
- Glucose, insulin, and C-peptide to study insulin sensitivity and β cell function^{72, 73} at both study visits.
- Blood cell counts.

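### Under prednisone, OGTT status is aliased with time since dose, so a difference between the GC responses with and without OGTT cannot be attributed to glucose

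*Combined protocol and SAP*

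**What the plan says.** Section 3.0 states the intention to "study PBMCs gene expression response to a glucose challenge due to" in vivo GC, as a way into the genetics of metabolic complications. Section 10.0 carries this into the last variant step, which combines genotype and expression data "to identify which variants do affect gene expression profile with GC administration with and without OGTT". It does not say whether these are two separate analyses or a comparison of one condition with the other.

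On timing, Section 6.0 says of Visit 2 that the first "collection will be performed around 4 hours after the ingestion of prednisone, and immediately after an OGTT will be performed". It continues: "Blood collection will occur at 10, 20, 30, 60, 90, and 120 minutes after glucose ingestion". Section 7.0 agrees with that span; the study team will "monitor them for the next 6-6½ hours after the administration of the drug". At Visit 1, without prednisone, "we will collect blood samples around 4 hours after the" participant's arrival, and the same OGTT draws follow. Participants excluded from the OGTT at Visit 1 for high fasting glucose have a different schedule: "blood will be collected approximately 4 and 6 hours after the fingerstick". No matching 6-hour draw without OGTT is described for Visit 2.

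The Measurements list in Section 6.0 says that RNA comes from PBMCs taken at both visits, without naming the draws. The differential-expression model in Section 10.0 adjusts for batch, age and BMI, and has no term for time since dose.

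**The concern.** At Visit 2 a sample cannot be under OGTT without also being later after prednisone. If the GC response of a gene changes between the two draws for any reason, that change appears in a with-versus-without-OGTT comparison exactly as a glucose effect would.

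Section 3.0 gives a reason to take this seriously. It reports that an earlier in vivo study "found that peak changes in gene expression were observed 4 hours after GC administration", which is the time of the sample without OGTT. Section 3.0 speaks of a response to a glucose challenge, and Section 10.0 uses hyperglycemic medium to stand in for the OGTT, so a glucose interpretation is clearly intended. At stake is the labelling of the output: genes or variants that govern how the GC response develops over time could be carried forward as glucose-dependent.

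**Working it through.** The plan gives no figure for this comparison, so there is none to reproduce. The power statement in Section 10.0 concerns differential expression and does not enter here.

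**1. Clock arithmetic (Section 6.0, Visit 2).** Without OGTT: about 4 h after prednisone. With OGTT: 4 h + 10 min to 4 h + 120 min, that is about 4 h 10 min to 6 h.

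**2. What each sample contains.** On the log2 scale, let m be the baseline, c the clock-time change between the two draws, o the OGTT main effect, g the GC effect at about 4 h, i the GC x OGTT interaction, and d the change in the GC effect between the two draws.

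| Sample | Expected log2 expression |
|---|---|
| Visit 1, 4 h, no OGTT | m |
| Visit 1, later draw, OGTT | m + c + o |
| Visit 2, 4 h, no OGTT | m + g |
| Visit 2, later draw, OGTT | m + c + o + g + i + d |

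Then, Visit 2 minus Visit 1:

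- GC response without OGTT = g
- GC response with OGTT = g + i + d
- Difference between them = **i + d**

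Visit 1 cancels c and o. It cannot cancel d, because no dose is given at Visit 1. Each response on its own is a valid GC effect for its own condition and time.

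**3. Identifiability.** There are six parameters and four cells, and the design matrix has rank 4. Only the sums c + o and i + d can be estimated. A larger sample or further covariates do not change the rank. Adding cells at 6 h without OGTT at both visits would raise it to 6.

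**4. Size, for illustration.** Set i = 0 and let a fraction f of the response fade, so d = -f x log2(fold change). For the 2.5-fold change used in Section 10.0, log2(2.5) = 1.322. The fractions are assumptions; the documents give none.

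| Assumed fade f | d (2.5-fold) | Apparent OGTT ratio (2.5-fold) | Apparent OGTT ratio (4-fold) |
|---|---|---|---|
| 0% | 0 | 1.00 | 1.00 |
| 10% | -0.13 | 0.91 | 0.87 |
| 25% | -0.33 | 0.80 | 0.71 |
| 50% | -0.66 | 0.63 | 0.50 |

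A response still rising would bias the other way: a 20% increase gives +0.26 log2, a ratio of 1.20.

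**5. Variants.** If a variant has per-allele effect b on the 4-hour GC response and that effect fades by f, the apparent variant x OGTT effect is (1 - f)b - b = -f x b, with no glucose effect at all.

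**6. Would it be noticed?** Take 40 participants (Section 2.0), all completing the OGTT, and an assumed SD of 0.5 to 1.0 for the within-person log2 difference in responses. For a 2.5-fold gene, a 20% fade gives z = 0.264 x sqrt(40)/SD = 3.34 to 1.67, hence a 92% to 39% chance of crossing nominal two-sided 0.05. A 10% fade gives 39% to 13%. These are single-gene figures, not the plan's FDR threshold.

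**The case against.** The strongest reply is that Section 10.0 defines no difference between the two conditions. It can be read as two analyses, each comparing Visit 2 with Visit 1 at the same point of the schedule, and step 2 shows that time since dose does not bias those. This stands. The problem arises only when the two are compared, or when a result found in one and not the other is credited to glucose.

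Three stronger conclusions are tempting, and the documents do not support them.

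- **That fading of the response will be misread as a glucose effect.** The 4-hour peak comes from one small study whose title (reference 71) names hydrocortisone. An overall peak does not fix the course of each gene, and nothing establishes the size or sign of d for oral prednisone. If the response merely tracked the 18 to 36 h half-life in Section 7.0, an imperfect proxy, two hours would lose 1 - 2^(-2/18) = 7.4% to 1 - 2^(-2/36) = 3.8%. The ratio for a 2.5-fold gene would then be 0.93 to 0.97, milder than the 10% row above.
- **That the gap is two hours.** The RNA draw is not named. An early post-glucose draw leaves the aliasing in place but shortens the interval.
- **That the metabolic-toxicity half of the Aim depends on this comparison.** Section 10.0 also regresses changes in metabolic indexes on each gene's log2 fold change. Both visits follow the same OGTT schedule, so that analysis does not need the comparison.

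It is also fair to say that this is a hypothesis-generating pilot. That lowers the stakes but does not make a mislabelled candidate harmless to whatever follows.

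**Conclusion.** The concern holds as a limit on interpretation. On the planned schedule, GC x OGTT and GC x time since dose are completely aliased in vivo, and Visit 1 does not separate them. This follows from the schedule alone. It does not show that the bias is present, or which way it goes: the apparent ratios of 0.91, 0.80 and 0.63 rest on assumed fades of 10%, 25% and 50% in a 2.5-fold response with no glucose effect, and no change over the interval would give a ratio of 1. The separate GC responses and the regression on metabolic indexes are untouched. What the plan cannot support is a statement that a gene or variant is glucose-dependent under GC because its response differs with and without OGTT.

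**What to change.** In Section 10.0:

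- Name the draws that supply RNA at each visit.
- Define two contrasts, each Visit 2 against Visit 1 at the matched time: the GC response at about 4 h, and the GC response at the named post-glucose draw (up to about 6 h after prednisone and 2 h after glucose).
- State that any difference between them will be reported as OGTT plus additional time since dose, not as a glucose effect.
- Use the in vitro comparison of the two glucose media, where GC exposure is fixed at 4 h, as supporting evidence. It should not be a required condition: Section 3.0 itself warns that culture alters expression, so a strict requirement could discard real in vivo effects.

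Optionally, describe at Visit 2 the 6-hour draw that Visit 1 already has for participants excluded from the OGTT, so that those samples have a pair. This would not resolve the aliasing. Section 4.0 excludes a fasting glucose of 126 mg/dl or more, so these participants should be few, and they are selected for high glucose.

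The cost is a few sentences, and a few tubes if the optional draw is taken. The downside is a narrower claim about glucose dependence.
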